# 7.3 Cognition and HRQoL in HGG

Cognitive dysfunction, whether it develops due to the underlying tumor, treatment, or use of medications such as anti-epileptics and corticosteroids, usually comes in concert with a reduction in HRQoL. In both newly diagnosed and recurrent HGGs, reduction in cognitive function was associated with a reduction in reported HRQoL [11-13]. When compared to healthy controls or patients with other malignancies, high-grade glioma patients experience a great degree of cognitive impairment and related reduction in HRQoL [13].

Before and during treatment for HGG, adult patients experience a decline in perceived HRQoL[14,15]. Liu defines HRQoL as "a concept that encompasses the multidimensional well-being of a person and reflects an individual's overall satisfaction with life" [15]. For brain tumor patients, focal neurological dysfunction, whether cognitive or physical, fatigue associated with treatment, symptoms such as nausea and anorexia associated with treatment, and other common symptoms such as insomnia, seizures, and headaches all have negative impacts on HRQoL. Overall, functionality and HRQoL are particularly important in brain tumor patients since these patients have more dysfunction in these areas than age-matched controls with non-small lung cancer [13]. In a large prospective study by Budrukkar and colleagues of HRQoL in brain tumor patients, they found that HRQoL, as rated by scores from questionnaires, was low before starting any type of treatment, and factors associated with poorer HRQoL included patients with poor performance status, illiteracy, and a more aggressive nature of the tumors [16]. Moreover, HRQoL is dependent upon the physical function and cognition of the brain tumor patients with better physical function and better cognitive

function reported having a higher level of HRQoL [11]. Liu and colleagues discuss how these symptoms and signs are interrelated and should not be studied alone because cognitive decline/ dysfunction were associated with increased fatigue and poorer performance status [15,17,18]. During concurrent chemoradiation, brain tumor patients experience a decline in relative HRQoL particularly due to fatigue and changes in cognition [7,19].

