In order to capture fully the many aspects of cognition and HRQoL, we have utilized both objective and subjective measures to evaluate issues with cognition, fatigue, HRQoL, and mood. Cognition can be measured objectively with standardized cognitive testing. One testing model is CNS Vital Signs®, a computerized battery. CNS Vital Signs® has been validated and is being used extensively in our research, not only primary brain tumor patients, but also patients with other forms of cancer [20]. Modalities within CNS Vital Signs® assess cognitive flexibility, complex attention, executive functioning, psychomotor speed, processing speed, verbal and visual memory. We published the cognitive performance of newly diagnosed HGG using this battery and showed that they had measurable cognitive dysfunction in all domains [21,22]. After diagnosis, newly diagnosed HGG patients exhibit deficits in all tested cognitive domains with standardized scores ranging from 90.1 to 72.7 (a score of 100 represents mean standardized score for normative age-matched subjects). These deficits continue throughout the treatment and disease trajectory with lower performances present after radiotherapy and 24 weeks after initial diagnosis. Importantly, performance on neurocognitive testing is independent of education, grade, gender, and tumor location, but Karnofsky Performance Scale (KPS) and surgery extent are important predictors of neurocognitive performance. Moreover, long-term survivors of primary HGG (WHO grade IV) continued to exhibit cognitive dysfunction despite having achieved an improved survival [23]. Therefore, there is an unmet need to improve the cognitive outcomes in patients with newly diagnosed HGG, irrespective of survival outcomes. Another testing model called The Brief Assessment of Cognition (BAC) is a battery of tests is implemented through an iPad-based app (VeraSci). The BAC was created by Richard Keefe, Jim Gold, Terry Goldberg, and Philip Harvey as a pen-and-paper measure for the repeated assessment of cognition in clinical trials for schizophrenia (referred to as BACS) [24]. With published normative data [25] and over a decade of use, the BACS is the subject of approximately 100 peer-reviewed papers and has been used in over 30 multisite clinical trials across a range of patient groups. To reduce rater burden and promote standardization of neurocognitive testing in clinical trials, the BAC is now implemented as an iPad-based app [26]. The BAC App assists raters in administration and scoring of all subtests included in the original pen-and-paper instrument.

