# **13.1** Screening Examination

The screening examination will take place between Day -21 and -1. An informed consent must be signed by the patient before any study specific screening procedures take place. Information collected prior to the signing of informed consent according to standard of care for procedures such as KPS, labs, history and physical, and MRI, etc. may be used to determine eligibility. Subject data to be collected at the Screening Examination is listed in the table above and includes physical and neurological examination; vital signs and weight; ECG, laboratory studies (complete blood count with differential, complete metabolic panel, PT/aPTT, and beta-HCG); past medical history; and concomitant medications (including but not limited to steroids and anticonvulsants). Additional

baseline testing will be completed for the following: cognitive testing, HRQoL Measurements, and hair loss evaluation.

The screening MRI or CT scan will be uploaded to the Duke central core for final review of eligibility. This will be required for all subjects. The clinical centers will be notified of the final determination of eligibility prior to the subject completing any study visit.

The pathology report used to determine eligibility, which includes any tumor markers will be redacted and uploaded to the sponsor electronic data capture system.

If a subject is found to be ineligible to participate in the study, the patient will not be randomized to a treatment arm and minimal records regarding the subject and the reason for screen failure will be retained.

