#### 16.5.2.1 Secondary Objective #1 for Phase 2: Cognition

The key secondary objective includes an evaluation and comparison of cognition among patients newly diagnosed with HGG and whether the addition of BMX-001 to standard RT and TMZ impacts cognition. This secondary endpoint is the mean change in cognitive functioning between baseline and week 24 within each treatment arm. The baseline measure is the last assessment obtained before initiation of standard chemoradiation.

Analysis of covariance will be conducted to compare treatment groups with respect to the change in cognitive function. The outcome of this model is change in cognitive function. Treatment group assignment will be included in the model as a predictor, and the baseline measure of cognitive function will be included as a covariate. Additional analyses will explore the impact of BMX-001 on cognition within patient subgroups defined by WHO grade and histological subtype.

Measurement of cognition will continue after initiation of adjuvant temozolomide. Longitudinal analyses will compare treatment arms with respect to the pattern of cognitive change observed over time. Initially a repeated measures analysis will be conducted. However, a significant amount of the follow-up cognitive assessments may be missing due to health decline, disease progression, and death. The patterns of "drop-out" in the two treatment arms may also differ. To address these problems, additional analyses will be conducted. These analyses may focus on only assessments with relative complete data, or may consider alternative analytic methods such as pattern mixture models.

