6 ANALYSIS POPULATIONS

The following populations will be identified:

• Intent to Treat Population (ITT): All patients randomized into the clinical trial, regardless of compliance.

¹ During study accrual, a new WHO classification system for CNS tumors was published [1]. Though the classification system in use at the time of study activation was used throughout the conduct of the study, the classification of all patients under the new WHO 2021 system will also be described.

- Safety Population: All patients who received at least one dose of BMX-001 or temozolomide
- Treated Population: All patients who completed chemoradiation with or without BMX-001. BMX-001 must be given for at least 6 weeks (or 13 doses).
- PK Population: Subjects who participated in the PK portion of the study (n=6).

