9.3 METHOD OF ANALYSIS

For the analysis of change in cognition between baseline and week 24, an analysis of covariance (ANCOVA) will be conducted to compare treatment groups within the treated patient cohort. The outcome of this model is change in cognitive function. Treatment group assignment will be included in the model as a predictor, and the baseline measure of cognitive function will be included as a covariate.

As noted earlier, a significant amount of the follow-up cognitive assessments may be missing due to health decline, disease progression, and death. Much of the missing data is due to a subject permanently dropping out of the longitudinal assessment. A linear random coefficient model stratified by drop-out pattern will assess whether cognitive changes over time are consistent across treatment groups and drop-out patterns. This pattern-mixture model accounts for within subject correlation of longitudinal assessments.

If assumption for conducting either the ANCOVA model or the pattern mixture model are not satisfied, alternative approaches to analyses may be conducted. Options include transformation of the outcome data, as well as use of nonparametric methods.

Given that numerous endpoints will be examined that relate to cognition, adjustments for multiple comparisons (e.g., false discovery rate methods or Bonferroni) may be considered.

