9.4.2 REVISED POWER ANALYSIS

Collection of measures of health-related quality of life and cognition is plagued with mistiming and drop-outs due to factors described in Section 9.1.

For the purpose of the analyses that focus on the change in cognition between baseline and week 24, the follow-up assessment should have occurred within +/- 4 week window of the scheduled week 24 assessment.

With this adjustment, there are 94 patients (52 in Arm A and 42 in Arm B) that has pre- and post-measurements of cognitive function. Assuming a standard deviation of 30 units, a two-tailed t-test conducted at the 0.05 level of significance (two-tailed) will have 80% power to detect a difference of 17.6.

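### The week-24 cognition ANCOVA adjusts for baseline score only, leaving out collected baseline factors that the protocol links to cognition; the two-term model is valid, and the likely gain from adding them is modest

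*SAP*

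**What the plan says.** Protocol 16.5.2.1 gives cognition special standing: "The key secondary objective includes an evaluation and comparison of cognition among patients newly diagnosed with HGG". Protocol 16.5.2.1 and SAP 9.3 specify the same model for change to week 24, with arm and baseline score as the only terms: "Treatment group assignment will be included in the model as a predictor, and the baseline measure of cognitive function will be included as a covariate". SAP 9.3 says the ANCOVA "will be conducted to compare treatment groups within the treated patient cohort". SAP 9.2 also requires an assessment within 4 weeks either side of week 24. SAP 9.4.2 reports the resulting number: "there are 94 patients (52 in Arm A and 42 in Arm B) that has pre- and post-measurements of cognitive function".

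Protocol 7.3 names other influences on cognition. One sentence begins "Cognitive dysfunction, whether it develops due to the underlying tumor, treatment, or use of medications such as anti-epileptics and corticosteroids"; another says that "Karnofsky Performance Scale (KPS) and surgery extent are important predictors of neurocognitive performance". These factors are recorded. Protocol 13.1 lists, among the screening data, "concomitant medications (including but not limited to steroids and anticonvulsants". KPS is in the screening schedule (Protocol 13, Table 4), and SAP 5 lists both KPS and extent of resection as characteristics to summarise by arm. Protocol 9.1.9 stratifies randomisation by WHO grade and institution.

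No cognition model in the SAP names KPS, extent of resection, steroids or anticonvulsants. SAP 9.5 adds WHO grade and tumour markers in further analyses only. The pattern-mixture model in SAP 9.3 is stratified by drop-out pattern and names no clinical covariates.

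**The concern.** The protocol identifies factors that bear on cognition and the trial collects them, but the main comparison on the key secondary objective does not use them. Prognostic baseline covariates normally sharpen an ANCOVA. They also guard against measured imbalance, which matters more here because randomisation protects the randomised set and not the analysed one.

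To be analysed, a patient must count as treated and have a usable assessment around week 24. If the treated cohort is the Treated Population of SAP 6, which I assume, Arm A also carries a condition with no counterpart in Arm B: "BMX-001 must be given for at least 6 weeks (or 13 doses". SAP 9.3 attributes missing assessments to declining health, progression and death. KPS, steroid need and extent of resection are plausibly related to all three. At stake are some precision and some protection of the treatment estimate against imbalance in factors already in the database.

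**Working it through.** **The plan's own figures.** Inputs from SAP 9.4: SD 30, two-sided alpha 0.05, power 80%.
- SE of the difference = SD × √(1/n₁ + 1/n₂). For 52 v 42 this is 30 × √(1/52 + 1/42) = 6.22.
- Detectable difference by noncentral t on 92 df: 17.62 (SAP: 17.6). The normal approximation gives (1.960 + 0.842) × 6.22 = 17.4.
- For 60 v 60 the noncentral t gives 15.47 (SAP: 15.5).

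Both figures reproduce, so the point concerns model specification and not arithmetic.

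**What 17.6 represents.** It is a two-sample t-test figure using the SD of a single assessment, with no credit for baseline score. The planned ANCOVA contains baseline score, so its detectable difference is smaller by a factor √(1 − r²), where r is the baseline to week-24 correlation. The documents do not give r. If r were 0.5 to 0.7 (assumption, with SD 30 at week 24), the two-term model would detect 17.6 × √(1 − 0.25) = 15.2 down to 17.6 × √(1 − 0.49) = 12.6.

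**Gain from further covariates.** Let R² be the share of variance left after baseline score that they explain. The detectable difference is multiplied by √(1 − R²), whatever r is. The documents give no R², so a range is assumed.

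| R² | √(1 − R²) | Relative fall | From 15.2 | From 12.6 |
|---|---|---|---|---|
| 0.05 | 0.975 | 2.5% | 14.8 | 12.3 |
| 0.10 | 0.949 | 5.1% | 14.4 | 12.0 |
| 0.20 | 0.894 | 10.6% | 13.6 | 11.3 |

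**Cost in degrees of freedom.** Grade 1, KPS as a linear term 1, extent of resection 2 (three categories in SAP 5), steroids 1, anticonvulsants 1: six in total. The effect on power is negligible. On the t-test scale, losing five df at R² = 0.05 gives 17.19, against 17.62 × 0.975 = 17.18 with none lost.

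**Room for imbalance.** For a binary factor with prevalence p, the chance SD of the between-arm difference is √(p(1 − p)(1/n₁ + 1/n₂)).
- 52 v 42: 9.5 percentage points at p = 0.3 and 10.4 at p = 0.5 (prevalences assumed).
- 80 v 80, p = 0.5: 7.9 points.

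**Bias if selection produces an imbalance.** Bias = imbalance × effect of the factor on week-24 score given baseline score. Both are assumed; the error rate uses SE 6.22.

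| Imbalance | Effect | Bias | Two-sided type I error |
|---|---|---|---|
| 10 points | 5 units | 0.5 | 5.1% |
| 20 points | 10 units | 2.0 | 6.2% |
| 30 points | 15 units | 4.5 | 11.2% |

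The SE of the planned ANCOVA is smaller than 6.22, so the same bias would weigh somewhat more there.

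**Retention by arm.** Against the goal of 80 per arm: 52/80 = 65.0% v 42/80 = 52.5% (chi-square p = 0.11). Against the 78 and 71 who received protocol treatment (SAP 10.3.2): 66.7% v 59.2% (p = 0.34). The SAP does not state the number randomised per arm, so 80 is the goal and not a count.

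**The case against.** The strongest reply is that Protocol 7.3 speaks of level of performance and not of change given baseline score. Its statement on KPS and surgery comes from a different battery (CNS Vital Signs; Phase 2 uses the BAC). The baseline assessment follows surgery and reflects entry KPS and current medication, so it absorbs part of these effects. Eligibility narrows them further: KPS at least 70, a definitive resection with residual enhancement of at most 3 cm, and stable or decreasing steroids. All of this stands, and it is why the gain is likely to be modest.

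Second, the SAP does not ignore drop-out. SAP 9.1 compares it by arm and looks for its predictors, and SAP 9.3 adds the pattern-mixture model. That is correct, but neither step puts these factors into the treatment comparison.

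Third, the two-term model is the protocol's stated analysis in an open-label trial. Protocol 16.5.4 scheduled looks at week-24 neurocognition in the first 80 patients, and the SAP already counts evaluable patients by arm. A late change of model can look data-driven. That stands as a reason to date and justify the change and to keep the two-term result in view.

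A reader might infer more than the documents support:
- That the two-term comparison is confounded. No imbalance is documented, chance imbalance is already covered by the nominal type I error, and the retention gap is not significant on either denominator.
- That adjustment lowers the detectable difference from 17.6 to about 15.7. That scales a figure without baseline adjustment by a variance share defined after baseline adjustment.
- That baseline covariates cure the selection. They address measured factors only.

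**Conclusion.** The point holds as an improvement to the specification and not as an error that invalidates the analysis. The main cognition model omits four collected factors that the protocol relates to cognition, and one randomisation factor, in a 52 v 42 subset formed after randomisation. The cost is some lost precision and no adjustment for whatever measured imbalance that subset contains.

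The size is a relative fall of about 3-11% in the detectable difference of the planned ANCOVA, resting wholly on an assumed R² of 0.05-0.20 beyond baseline score. The absolute value cannot be given because the documents do not state the baseline to week-24 correlation. The bias figures rest on assumed imbalances and effects. They show that the middle case is small (2 units against an SE of 6.22) and that only a large imbalance in a strong factor would matter much. Bias from drop-out due to decline, progression or death remains either way.

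**What to change.** Before database lock, and before any further comparison of cognition by arm, amend SAP 9.3 to:
- Fit the week-24 ANCOVA with arm, baseline score, WHO grade as randomised, baseline KPS, extent of resection, baseline systemic corticosteroid use (yes/no) and baseline anticonvulsant use (yes/no).
- Use the same baseline covariates in the pattern-mixture model.
- Report the protocol's two-term ANCOVA alongside.
- Tabulate these factors by arm in the 94 analysed patients. SAP 5 does not list steroids or anticonvulsants, and the concomitant-medication table in SAP 19 covers the Treated set only.
- Use baseline values only. Protocol 9.1.6 allows steroids to be added later, and use after randomisation could itself be affected by treatment.

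Grade enters because it is a randomisation factor; Protocol 7.3 says performance is independent of it. Institution, the other stratification factor, could cost up to 10 df (Duke plus up to 10 sites), so leaving it out is reasonable, but the SAP should say so.

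The cost is SAP wording and programming, up to six degrees of freedom in 94 patients (fewer if the biopsy-only category is empty, as inclusion criterion 4 suggests it may be), and a departure from the protocol's stated model. In an open-label trial, that departure must be dated and justified, with a statement of what cognition data by arm had been seen by then.

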# 7.2 Radiation-Induced Damage during Brain Tumor Treatment

During the disease treatment course, the nervous system can be damaged by all parts of the multimodal approach. In particular, RT can lead to the generation of reactive oxygen species which in turn leads to oxidative stress [4]. The oxidative stress is not only responsible for the damaging of the DNA and killing of the tumor cells but also leads to damage of the white matter [5]. Central nervous system toxicity from RT is defined as acute, early delayed, and late delayed [6]. Acute form can occur during RT and is more apparent with doses > 60 Gy. This is rarely seen with the modern approach to standard chemoradiation in adult glioma patients. Early delayed encephalopathy and late delayed encephalopathy are still seen with some frequency in the HGG population. Early delayed encephalopathy is characterized clinically by somnolence, attention deficits, and gait impairment. This occurs between one to six months after RT and is thought to be due to transient demyelination. Late delayed encephalopathy occurs months to years after RT and, clinically, patients demonstrate a pattern of subcortical dementia (short-term memory loss, problems with gait and attention). Mechanism of action involves damage to the supporting vasculature, which in turn leads to demyelination and, in severe cases, RT necrosis. The impact to patients is cognitive impairment and subsequent degradation of HRQoL. In fact, 50-90% of brain tumor patients that received RT demonstrated cognitive impairment, if they survived >6 months from RT [7-10]. In summary, the oxidative stress produced by RT in brain tumor patients leads to white matter damage, subsequent cognitive impairment, and finally quality of life impairment.

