9.1 DROP-OUT PATTERNS

The ultimate goal of this objective is to compare groups with respect to longitudinal changes in cognition over time. Unfortunately, due to the patient population that are eligible to participate in this study, a significant amount of the follow-up cognitive assessments may be missing due to health decline, disease progression, and death. Some of the missing data may be intermittently missing (i.e., missing observations between observed assessments); however, much of the missing data will be "drop-out" (i.e., subject permanently drops out of longitudinal assessment). The pattern of "drop-out" in the two treatment arms will be assessed.

The proportion of patients within each treatment arm who lack assessments after the baseline assessment will be determined and compared using a chi-square test. We will also explore whether there are subgroups defined by clinical, cognitive, or HRQoL data that are predictive of a subject lacking a post-baseline assessment.

Drop-out may also occur after one or more follow-up assessments are completed. The relationship between the time of the last completed assessment and treatment group will be assessed via a contingency table and chi-square test.

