9.2 ENDPOINT

Though the study is a longitudinal analysis, the initial focus of the analyses of this objective is an examination of the mean change in cognitive functioning between baseline and week 24 (occurs after completion of RT) within each treatment arm. The baseline measure is the last assessment obtained before initiation of standard chemoradiation.

There is variability in the timing of follow-up measurements. For the purpose of this analysis a +/- 4 week window will define the 24 week assessment.

Clearly a patient without an assessment post-baseline will not be included in these analyses. Analyses described in Section 9.1 explore how the patients excluded from analyses differ from those who are included in analyses.

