15.2 METHOD OF PRIMARY ANALYSIS

The analyses that will be conducted are similar to those described in Section 9.3. For the analysis of change in HRQoL between baseline and week 24, an analysis of covariance will be conducted to compare treatment groups. The outcome of this model is change in cognitive function. Treatment group assignment will be included in the model as a predictor, and the baseline measure of HRQoL function will be included as a covariate.

A linear random coefficient model stratified by drop-out pattern will assess whether HRQoL changes over time are consistent across treatment groups and drop-out patterns. This pattern-mixture model accounts for within subject correlation of longitudinal assessments.

If assumption for conducting these analyses fail, alternative analytic approaches will be considered include, a transformation of the outcome data, or nonparametric methods.

Given the number of HRQoL tests that will be conducted, p-values will be adjusted for multiple comparisons.

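### The only longitudinal model for cognition and HRQoL reads as a straight line in time, which suits a fall after radiotherapy poorly and can create false differences between drop-out patterns

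*SAP*

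**What the plan says.** SAP 9.1 sets the aim for cognition: "The ultimate goal of this objective is to compare groups with respect to longitudinal changes in cognition over time". SAP 9.2 then says that "the initial focus of the analyses of this objective is an examination of the mean change in cognitive functioning between baseline and week 24", and 9.3 analyses that change by ANCOVA with baseline as covariate. This is the only cognition analysis with a power statement (9.4).

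For the longitudinal aim, SAP 9.3 gives one model: "A linear random coefficient model stratified by drop-out pattern will assess whether cognitive changes over time are consistent" between arms and between drop-out patterns. SAP 15.2 does the same for HRQoL: "A linear random coefficient model stratified by drop-out pattern will assess whether HRQoL changes over time are consistent across treatment groups and drop-out patterns". Neither section defines time, mentions a curve, knot or visit factor, says whether baseline is a response or a covariate, or defines the patterns and their weights. If assumptions fail, 9.3 and 15.2 name outcome transformation and nonparametric methods as options.

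Protocol 16.5.2.1 had a different first step: "Initially a repeated measures analysis will be conducted". Pattern-mixture models were a possible addition. The SAP does not carry that first step forward, and SAP section 3 makes the SAP govern where methods differ substantially.

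On the expected course, Protocol 7.2 says of early delayed encephalopathy: "This occurs between one to six months after RT and is thought to be due to transient demyelination". It calls the acute form rare with modern treatment and places late injury months to years after RT. Protocol 7.3 reports lower cognitive scores after radiotherapy and at 24 weeks from diagnosis, and falling HRQoL during chemoradiation.

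**The concern.** Radiotherapy lasts six weeks and the first post-baseline assessment comes 2 to 4 weeks after it ends. A loss caused by treatment would therefore show mainly as a fall between the first two visits, followed by a plateau, partial recovery or later decline. A model with one intercept and one slope per patient cannot show that shape.

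Two things are at stake. First, the slope fitted to a fall-then-plateau course depends on how long the patient was followed. Early drop-outs contribute only the fall; completers contribute the fall and a long flat stretch. Stratifying by drop-out pattern then shows different slopes even if every patient follows the same curve, and the model's stated purpose is to judge consistency across patterns. Second, an arm difference that arises early and stays constant is spread over a year as a shallow slope difference and becomes harder to detect.

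**Working it through.** **1. The plan's own figures.** Detectable difference at 80% power, two-sided 0.05, SD 30 (SAP 9.4):
- 52 v 42: (1.960 + 0.842) × 30 × √(1/52 + 1/42) = 17.4 by the normal approximation, 17.62 with t quantiles. SAP: 17.6.
- 60 v 60: 2.802 × 30 × √(2/60) = 15.3, or 15.47 with t quantiles. SAP: 15.5.

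Both reproduce. No operating characteristic is given for the longitudinal model.

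**2. Inputs.** From the documents: 52 v 42 patients, SD 30, a 17.6-point loss, visits about every 8 weeks (BAC App and HRQoL). Taken as weeks 0, 8, ..., 56. Assumed, because the documents do not give them: intraclass correlation 0.5-0.8; random-slope SD 10-30 points per year; five patterns (last visit week 8, 16, 24, 40 or 56) with shares of 20% each or 10/10/20/20/40%; drop-out unrelated to scores; baseline as a response.

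The 94 patients are those with a week-24 assessment, so they serve as a size only. A longitudinal model would also include patients who stopped earlier.

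**3. Slope by pattern under one common curve.** Every patient loses D = 17.6 at the first post-RT visit and stays there. With n visits spaced h = 8 weeks, the fitted slope per week is -6D / [h·n·(n+1)].

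| Last visit (week) | n | Slope per week | Per 24 weeks |
|---|---|---|---|
| 8 | 2 | -2.200 | -52.8 |
| 16 | 3 | -1.100 | -26.4 |
| 24 | 4 | -0.660 | -15.8 |
| 40 | 6 | -0.314 | -7.5 |
| 56 | 8 | -0.183 | -4.4 |

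The patients do not differ; only their follow-up does. If the decline really is linear (17.6 per 24 weeks), every pattern gives -17.6.

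**4. False pattern differences, one setting in full** (equal shares, correlation 0.7, slope SD 10 per year). Variance of one patient's slope = (10/52)² + 270/S, where 270 = 900 × 0.3 and S is the sum of squared visit deviations: 32, 128, 320, 1120, 2688. This gives 8.474, 2.146, 0.881, 0.278, 0.137. Weights with 18.8 patients per pattern: 2.22, 8.76, 21.35, 67.6, 136.8 (sum 236.7).

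The weighted mean slope is -0.3166 per week. Noncentrality = Σ weight × (slope - mean)² = 7.87 + 5.38 + 2.52 + 0.00 + 2.43 = 18.2. On 4 df at 5%, the test rejects 95% of the time although no pattern difference exists. Over all settings the range is 49-99%.

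**5. Arm comparison, same setting.** Arm B has the drop and Arm A does not. Information = 236.7 × (52 × 42)/94² = 58.5, so SE = 0.131. z = 0.3166/0.131 = 2.42, and power = Φ(2.42 - 1.96) = 68%. Over all settings: 34-83%.

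In every setting, visit as a factor (patterns pooled) did better: 62-99% for the 7-df arm-by-visit test and 58-98% for the week-24 contrast. In the setting shown these were 91% and 85%. A separate calculation with the same sample size, SD and loss gave slope 34-66% against 84-99% for a knot model read at week 24.

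**6. Weighting.** If pattern slopes are averaged by pattern share instead, power is 44-92%, close to the week-24 visit contrast. The estimate then follows the drop-out mix: with equal shares (52.8 + 26.4 + 15.84 + 7.54 + 4.4)/5 = 21.4 per 24 weeks, and with 10/10/20/20/40% it is 14.4, for the same 17.6-point effect.

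**7. Week-24 ANCOVA.** It uses no time line. For this effect its power is about 90-100% if the drop is still present at week 24.

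**The case against.** The strongest reply is that the SAP never says straight line. Linear can mean linear in the parameters; Protocol 16.5.2.2 speaks of mixed linear models in that general sense, and a random coefficient model with a knot is still linear. That stands in part: the firm defect is an undefined time function, and the straight line is only its natural reading. If baseline were a covariate and only later visits were modelled, the early fall would enter the arm intercept. The SAP settles none of this.

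Second, the week-24 ANCOVA is the initial and only powered analysis. That stands in full. A reader might infer that the plan cannot detect a cognitive benefit; it can, if the benefit is present at week 24.

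Third, a reader might infer that the slope comparison is almost blind to BMX-001, or even points the wrong way, because the injury is transient. With assumed curves that recover by week 32 or 40 and inverse-variance weights, power for benefit is indeed about 0-13%. The documents do not support building on this. Transient describes demyelination in Protocol 7.2, not test scores; Protocol 7.3 points to deficits that continue; no recovery time is stated. With weights equal to pattern shares, the same curves give 9-79% with the right sign.

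Fourth, the fallback options in 9.3 are not exhaustive, and a random coefficient model is itself a repeated-measures method. Both are true, but neither fixes the time shape in advance.

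Fifth, patients last seen at the post-RT visit carry no information on later time terms, so flexible time cannot simply be copied into every pattern. That stands, and the fix allows for it. The paper tests have only four planned timepoints, so the slopes in the table apply to the BAC App and HRQoL schedule.

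**Conclusion.** The point holds as a specification fault in a supporting analysis. As naturally read, the only longitudinal model for cognition and HRQoL assumes a constant rate of change that the protocol's own account of the course makes unlikely. Transience is not needed for this: one persistent drop shared by all patients yields slopes that differ about twelvefold by follow-up (52.8/4.4 = 12), and a nominal 5% consistency test that rejects about 50-99% of the time. Slope power for a persistent 17.6-point arm effect is about 34-83% with inverse-variance weights. If the effect recovers, slope power is lower still, by an amount that depends on the assumed curve and weighting.

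The slope values are plain arithmetic given the curve and visit times. The rejection rates and powers depend on the assumed correlation, slope SD, pattern mix, baseline as a response, and drop-out unrelated to scores. Cognition is a secondary objective and HRQoL exploratory; neither the primary survival analysis nor the week-24 ANCOVA is touched. The change should be made, because the SAP calls this longitudinal comparison its ultimate goal and uses this model to address drop-out.

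**What to change.** In SAP 9.3 and 15.2:
- Restore the protocol's repeated measures analysis as a mixed model with windowed visit as a factor and arm-by-visit terms, or use a piecewise line with a knot at the first post-RT visit and arm effects in both segments.
- State whether baseline is a response or a covariate.
- Report the arm difference at week 24 and averaged over the post-RT to week-24 visits.
- Keep the pattern-mixture model as a sensitivity analysis with the same knot. Define the patterns and their weights. Group patterns so that each segment can be estimated, or state the identifying restriction for patterns that end at the post-RT visit. Compare patterns only over the time they share.

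This changes SAP text only and needs no new data. The price is a few more parameters, visit windows for data that SAP 9.4.2 admits are often mistimed, and a small loss of power if the true course is exactly linear.
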